This is a prospective randomized controlled trial investigating the therapeutic effect of the Hybrid Bracing Protocol(HyBP) over the Conventional Brace in enhancing In-brace Correction(IBC) for adolescent idiopathic scoliosis(AIS). Scoliosis is a complex three-dimensional spinal deformity and AIS is the commonest with a high prevalence of 2-4%. If left untreated, AIS can progress resulting in significant health problems including back degeneration and negative body images. Bracing, such as Underarm Brace(UAB) used in our center, is indicated for skeletally immature patients with Cobb angle $>20^{\circ}$. Another bracing system is a nighttime Lateral Bending Brace(LBB) designed in a bending position opposite to the convexity of the curve thus resulting in its overcorrection. If AIS becomes severe despite bracing, ultra-major surgery is indicated aiming at bony fusion of the deformed segment with instrumentation. It is therefore important to maximize treatment effectiveness with bracing to control curve progression and to avoid the need for surgery. In-brace Correction(IBC) is the percentage reduction in Cobb angle with bracing. Studies have reported IBC is an important determinant of brace effectiveness. For enhancement of IBC, we put forward the Hybrid Bracing Protocol(HyBP) combining the use of daytime UAB and nighttime LBB. To be best of our knowledge, HyBP has never been reported in the literature. Our pilot study on 8 patients treated with HyBP and 8 Cobb-matched historical controls treated with fulltime UAB showed very promising results with IBC of $42.1\pm22.0\%$ and $22.1\pm14.9\%$ in the HyBP and control group respectively. We therefore propose a formal prospective rater-blinded randomized controlled trial on 120 skeletally immature AIS female subjects with single thoracolumbar or lumbar curve newly prescribed with bracing. They are randomly allocated to the HyBP Group or the Conventional Brace Group (CB Group). The primary objective is to determine if the HyBP Group has better treatment effect in terms of In-brace Correction (IBC) when compared with the CB group at 3-month and 18-month after bracing. This is a 3-year study proposal representing the first phase of a project, to be followed by the second phase of the project when all subjects of the entire cohort will be assessed on curve outcome at time of completion of bracing and at 2 years post-bracing. This study will carry significant clinical impacts in that, if proven useful, the HyBP can be used for enhancement of treatment outcomes with bracing, thus preventing the scoliotic spine from deterioration and to avoid the need for surgery.

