Other than treatment with different bracing protocols, the same standard orthotic and medical care for treating scoliosis will be provided for both the CB Group and HyBP Group according to the SOSORT “Standards of management of idiopathic scoliosis with corrective braces in everyday clinics and in clinical research” [23]. Subjects are instructed to wear the brace 23 hours daily [6]. The rest hour is for bathing and exercises. Brace compliance in terms of the average number of hours per day of brace wear will be separately evaluated for the daytime UAB and nighttime LBB.

Study Visits, Investigations and Measurements:-

1. ***Study visits:*** Subjects will be evaluated at baseline just before bracing, 3 months and 6 months after bracing and at 6-monthly intervals thereafter (Figure 3 for details).
2. ***Plain radiography of the whole spine in standing position*** will be taken with a standard protocol using the EOS system:
 - a. Measurements are made as follows
 - i. PA view for measurement of:
 - a. Frontal Cobb angle of the structural curve [24, 25].
 - b. Trunk Shift will be measured in cm indicating the perpendicular distance of mid-point of T1 vertebra from the central sacral line [24],
 - c. Curve levels, apex levels, side of curves
 - ii. Lateral view for measurement of Cobb angle for thoracic kyphosis and lumbar lordosis

- b. Timing
 - i. At baseline, 3rd month, 6th month, then every 6 months thereafter
 - a. PA and lateral x-ray are taken without brace for monitoring of curve severity
 - ii. At 3rd month, and 18th month
 - a. PA and lateral x-ray is taken without brace, then followed by taken with the daytime UAB for evaluation of In-brace Correction
 - iii. (At completion of brace fitting, a supine AP x-ray of whole spine taken with LBB will be assessed with the frontal Cobb angle)
- c. In-brace Correction (IBC) = $(([\text{Pre-brace Cobb}] - [\text{In-brace Cobb}]) / \text{Pre-brace Cobb}) \times 100\%$. It will be evaluated at the 3-month and 18-month time-points
- d. *Radiographic measurements will be done by a single experienced rater who is blinded to subject's grouping (he will not be shown the x-ray taken with the LBB).*
3. Brace compliance monitoring :- data on brace usage from the aforementioned monitoring devices will be retrieved at each study visit. The body temperature collected from the sensor will be used for compliance analysis and 32° Celsius is set as the compliance threshold [26].
4. Quality of Life (QoL) Questionnaires :-

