This will be conducted according to the standard protocol at baseline and the 18-month time-point for self-administration of the following:
 - a. SRS-22r [27]
 - b. Spinal Appearance Questionnaire (SAQ) [28]
 - c. Brace Questionnaire (BrQ) [29]The Chinese versions for SRS-22r, SAQ and BrQ have all been validated and ready for use in this study [30-33].
5. Anthropometric and maturity assessment:-
Body weight, standing height, sitting height and arm span will be measured at each study visit according to the standard protocol. The “menarchal year”, defined in a way similar to that by Lehtonen-Veromaa et al [34], is the age at menarche subtracted from the current age (i.e., [current age – age of menarche] in years). For pre-menarchal subjects, the age of menarche is determined at subsequent study visits.

End of Brace Treatment :-

Brace treatment will be stopped with one of the following conditions:

1. At skeletal maturity: bracing will be stopped at maturity following a standardized protocol of weaning. Maturity is defined as [35]:
 - a. Risser sign 4 or more and
 - b. with no change in height or <1 cm change in standing height over 2 consecutive visits 6 months apart and
 - c. 24 months post-menarchal
2. When surgery for scoliosis is done. The indication for surgery in our center is Cobb angle > 55° despite treatment with braces.
3. If subjects decline further treatment with bracing of their own accord

Post-brace curve outcome and treatment success:- Apart from the primary objective of assessing IBC, effectiveness of bracing treatment will also be assessed with respect to post-brace curve outcome, ie curve severity after cessation of bracing treatment as follows:

1. Increase in Cobb angle $\leq 5^\circ$ for the structural curves at skeletal maturity
2. Cobb angle remains $\leq 45^\circ$ at skeletal maturity
3. Cobb angle remains less than surgical threshold of 55° at skeletal maturity

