Maintenance of Compliance :- Compliance with treatment protocol will be emphasized from time to time. To aim at a high level of compliance for both groups, we will explain to the patients and their legal guardians in details about the purposes of the study. Rapport is emphasized. Our RA will make regular phone contacts with the subjects of both groups to provide support and enquire about their situation, indicate concerns about their difficulties, answer any queries and remind them of the importance of adherence to the treatment protocol. We will also engage active participation of the parents. With experiences from previous clinical trials involving adolescent scoliosis subjects [22], we are confident that subjects will be compliant with the study protocol.

Persistence of study in COVID-19 pandemic environment:-

Research investigations are done during routine clinic visits. Since AIS subjects will need to come back for follow-up of their scoliosis even during a pandemic, this study will persist and not be affected even under the COVID-19 or other infection disease pandemic environment.

Statistical Analysis:-

The spread of data will be tested for normality. For data that is normally distributed, the numerical data are expressed as mean \pm SD. Otherwise they are expressed as median (interquartile range). Demographic data, anthropometric data, QoL scores, initial Cobb angle and other curve morphological data between the two groups at baseline will be compared using two-sided independent student's t-test or Chi-square test as appropriate.

To analyze treatment outcomes, the “Intention-to-Treat” approach is adopted. For the primary objective, two-sided independent student's t-test will be used to compare between-group IBC. For secondary objectives, Chi-square test will be used for comparing the proportions of successful treatment between the two groups. Logistic regression and linear regression model will be used for control of confounding from brace compliance and variables that are unbalanced at baseline between the study groups. QoL scores at the 18-month time-point for the two study groups will be compared with ANCOVA for adjustment of effect from baseline QoL scores. A p value of < 0.05 is considered statistically significant. SPSS 20.0 for Windows will be used for statistical analysis.

[figure not shown]
Sample size estimation:-

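### The 18-month IBC comparison is called intention-to-treat, but the t-test can use only girls with an 18-month in-brace film, and those who decline bracing or have surgery earlier have no planned route to one

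*Protocol*

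**What the plan says.** The protocol's opening summary sets the primary comparison of the Hybrid Bracing Protocol (HyBP) group "when compared with the CB group at 3-month and 18-month after bracing". Under Study Visits, Investigations and Measurements, the outcome at those two visits comes from paired films: "PA and lateral x-ray is taken without brace, then followed by taken with the daytime UAB for evaluation of In-brace Correction".

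The section End of Brace Treatment states that "Brace treatment will be stopped with one of the following conditions" and lists three: skeletal maturity, surgery for scoliosis, and "If subjects decline further treatment with bracing of their own accord". For the first, "bracing will be stopped at maturity following a standardized protocol of weaning".

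Under Statistical Analysis: "To analyze treatment outcomes, the “Intention-to-Treat” approach is adopted". The next sentence fixes the method: "For the primary objective, two-sided independent student's t-test will be used to compare between-group IBC". It names no time-point. Read with the summary, it means a t-test at each of the two visits.

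Sample size estimation requires 49 girls per group and enrols 60 to allow for about 20% dropout.

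**The concern.** A two-sample t-test uses only girls with an observed value. A girl who has declined bracing or had surgery before month 18 is no longer being treated in the UAB. No film in it is arranged for her, and no rule gives her a value. The population label and the test are both fixed in the protocol, and at month 18 they do not agree.

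The loss need not be neutral. The protocol's own literature review links poor IBC to unsatisfactory bracing outcome, so girls with low IBC may be the likelier ones to progress or give up. The arms also differ in what the girl is asked to wear: one brace, or a day brace plus a night bending brace. If stopping depends on IBC and does so differently by arm, the 18-month difference is biased in a direction that cannot be known in advance. The t-test at month 18 also ignores the 3-month IBC already recorded for girls who stop later.

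**Working it through.** **1. The plan's own sample size.** With effect size 0.8, two-sided alpha 0.025 and power 0.95, the normal approximation gives n = 2 × (2.241 + 1.645)² / 0.8² = 47.2, so 48 per group. The exact calculation with the noncentral t distribution gives 49, which matches the protocol. If 49 of 60 contribute, 11 of 60 (18.3%) per arm do not. The sizing therefore already expects some girls to add nothing to the test.

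**2. Is power the problem?** No. At effect size 0.8 and two-sided alpha 0.025, power is 94.8% with 48 per arm (20% loss) and still 91.4% with 42 per arm (30% loss). The issue is selection.

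**3. Which stopping conditions can remove the 18-month film?**

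- *Maturity.* Entry requires Risser 0 to 2 and, if post-menarchal, less than 12 months since menarche. Maturity requires Risser 4 or more, height change below 1 cm over two consecutive visits 6 months apart, and 24 months since menarche, all together. Visits fall at months 0, 3, 6, 12, 18 and 24. At month 12 the longest possible time since menarche is below 12 + 12 = 24 months, so the definition cannot be met. At month 18 it can be met only by girls who entered at 6 months or more (6 + 18 = 24). All others must wait until month 24 or later. The in-brace film is due at that same month-18 visit, and bracing then ends by weaning. Apart from a short gap between the eligibility check and the start of bracing, or a decision between visits, maturity does not act before the film.
- *Surgery.* Entry Cobb is at most 40° and the stated indication is above 55°, so more than 55 − 40 = 15° of progression is needed, with the operation done before month 18. This is possible but less likely.
- *Refusal.* It can happen at any time and is the main route.

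**4. How large could the shift be?** The protocol gives neither the share of girls who stop nor its link with IBC, so both are assumed. Let a share q of one arm stop, with correlation r between the tendency to stop and low IBC, while losses in the other arm are unrelated to IBC. For normally distributed IBC the mean of those remaining in the first arm moves up by

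shift = r × φ(z_q) / (1 − q), in SD units.

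The SD comes from the pilot table: √((22.0² + 14.9²) / 2) = 18.8 points. The design effect of 0.8 SD is then 0.8 × 18.8 = 15.0 points.

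| q | r | Shift (SD) | Shift (IBC points) | Share of 15.0 points |
|---|---|---|---|---|
| 5% | 0.3 | 0.033 | 0.6 | 4% |
| 10% | 0.5 | 0.097 | 1.8 | 12% |
| 20% | 0.5 | 0.175 | 3.3 | 22% |
| 20% | 1.0 | 0.350 | 6.6 | 44% |

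For the last row: φ(z_0.2) / 0.8 = 0.280 / 0.8 = 0.350, and 0.350 × 18.8 = 6.6. The sign depends on which arm loses its low-IBC girls. If both arms lost the same share with the same link, the shifts would cancel in the difference.

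**The case against.** The strongest reply has four parts.

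First, the protocol nowhere restricts the t-test to girls still in brace, and does not forbid filming a girl who has stopped. The month-18 films are scheduled by visit. This stands as far as it goes: a reader might infer that the protocol declares a still-braced population, and it does not. The available-case character follows from the test together with the lack of any planned film or value for these girls.

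Second, a reader might infer that all three stopping conditions take the outcome away, and in particular that girls more than 6 months past menarche at entry mature out before month 18. That looks at the menarche criterion alone. The visit schedule, the Risser and height criteria and the timing of the film defeat it, so the point rests on refusal and surgery only.

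Third, handling of missing values is commonly left to the analysis plan, which is not at hand and may deal with this. Silence alone would be no finding. But the protocol does state a population and a test, and that pair does not deliver intention-to-treat at month 18. If an analysis plan already resolves it, a cross-reference is enough.

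Fourth, no document shows more refusal in the HyBP group. The two braces are worn in turn, day and night, and the 23-hour instruction is stated without distinction by group. This stands: differential stopping is a plausible risk and has not been shown.

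**Conclusion.** The point holds in a limited form. At month 18 the fixed t-test compares girls who have an in-brace film, and girls who decline bracing or have surgery earlier drop out of a comparison labelled intention-to-treat. The 3-month comparison is little affected: only early refusal or, improbably, very early surgery could touch it.

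The size is unknown. The range of about 0.6 to 6.6 IBC points rests on assumed stopping of 5% to 20% in one arm, an assumed correlation of 0.3 to 1.0 with low IBC, normality, and the pilot SD from 8 girls per group. A reader might take the top figure, 44% of the design effect, as the expected bias. The documents do not support that. It requires one arm to lose exactly its lowest fifth while the other loses girls at random, and the protocol's 20% is a general dropout allowance for each group, not tied to IBC.

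The change is worth making because one of the two primary time-points is exposed and the remedy is cheap.

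**What to change.** Replace the separate t-tests with one mixed model for repeated measures of the 3- and 18-month IBC, with arm, visit, arm-by-visit and baseline Cobb angle, analysed as randomised. It gives an arm difference at each visit, and girls who stop after month 3 contribute their 3-month value.

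Alongside it:

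- Report the number of missing in-brace films by arm, visit and reason. Include girls with no in-brace film at all, since the model omits them too.
- Add a sensitivity analysis for departures from missing-at-random. One example sets 18-month IBC to 0 after refusal or surgery; under the protocol's formula, no brace means no in-brace reduction. This defines a different, composite outcome, so it should stay a sensitivity analysis. It should also cover girls who stopped before any film.
- Describe any observed-only 18-month result as a comparison among girls with an 18-month in-brace film.

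Nothing here alters when bracing ends. The cost is a few sentences in the protocol or analysis plan and slightly more analysis work, with no added visits, films or patients. The downside is that the main model relies on a missing-at-random assumption, which the data cannot confirm and the sensitivity analysis is there to probe.

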1. presenting with associated musculoskeletal, neurological or other conditions possibly responsible for the curvature
2. with previous surgical or orthotic treatment or
3. physical or mental disability that prevent patients from complying with the bracing protocol

An initial interview will be conducted with the subject and her legal guardians on details of the aims, the protocol and the timeframe of the study. Questions from the participants will be answered up to their satisfaction. An informed consent will be obtained. Ethical approval will be obtained from CREC (the IRB for our hospital) before the study is implemented. The study will be carried out in compliance with the Declaration of Helsinki and ICH-GCP.

Subject Randomization:- Assignment to a group is by a stratified randomization protocol with a permuted block of 10 to allow recruitment to be spread over 12 months. Allocation concealment is strictly followed to prevent investigators / subjects from knowing or predicting the next allocation. An individual sealed envelope containing the group allocation for the next subject will be open only after the subject agrees to participate and an informed consent is obtained.

The Conventional Bracing Group (CB Group):-

1. Brace fitting: The subjects in this group will be treated with the conventional rigid underarm brace (UAB) routinely used in our Center [19, 21] (Figure 1A). A CAD/CAM system (Vorum Research Corporation, Canada) will be used to capture the 3D information of patient's body and to design spinal orthosis through its purpose-design software [16, 17]. The pressure pads are strategically located based on the orthotist's experience in examining the apex of the rib hump and lumbar prominence and information from the software. After

the brace is ready, fine adjustment of location of the pressure pads will be made with reference to an in-brace whole spine radiograph.

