No similar study of this nature has been reported in the literature. According to our pilot study, the effect size is 1.065. Given the limitations with the pilot study as mentioned above, a more conservative and lower effect size of 0.8 will be adopted for sample size estimation. Assuming an alpha value of 0.025 and a statistical power of 0.95, 49 subjects are required for each group. Assuming a dropout rate of approximately 20% for each group, a total sample size of 120 subjects with 60 subjects in each group are required.

Figure 1A: The rigid underarm brace (Conventional Brace) used in this study

Figure 1B: Key pressure areas with paddings and the 3-point control system

In-brace Correction (IBC) with the Hybrid Bracing Protocol (HyBP)

Figure 2A: Before bracing

[figure not shown]
Figure 2B: x-ray taken with Lateral Bending Brace (LBB)

Figure 2C: x-ray taken with Underarm Brace (UAB)

Figure 3: Study flowchart

References

[2] Nachemson A. Adult scoliosis and back pain. *Spine*. 1979 Nov-Dec;4(6):513-7.

[3] Cobb JR. The problem of the primary curve. *Journal of Bone and Joint Surgery*. 1960 Dec;42-A:1413-25.

[4] Lonstein JE. Scoliosis: surgical versus nonsurgical treatment. *Clin Orthop Relat Res*. 2006 Feb;443:248-59.

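### The primary in-brace correction comparison is fixed as an unadjusted t-test; prespecifying adjustment for baseline Cobb and any named strata would be a cheap gain in precision, not the correction of an error

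*Protocol*

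**What the plan says.** In the Protocol, under Statistical Analysis, the primary objective is tested with a two-sided independent "t-test will be used to compare between-group IBC". No covariate is attached. Four other statements bear on this.

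- **Subject Randomization** describes the allocation as follows: "Assignment to a group is by a stratified randomization protocol with a permuted block of 10 to allow recruitment to be spread over 12 months". No stratification factor is named, and the only stated purpose is the spread of recruitment.
- **Study Visits, Investigations and Measurements, item 2b(i):** at baseline and later visits, "PA and lateral x-ray are taken without brace for monitoring of curve severity". Baseline Cobb is therefore available for every subject, and Statistical Analysis lists it among the variables to be compared at baseline ("initial Cobb angle and other curve morphological data between the two groups at baseline will be compared").
- **Statistical Analysis, regression sentence:** logistic and linear regression are planned for "control of confounding from brace compliance and variables that are unbalanced at baseline between the study groups". This follows the sentence on the secondary objectives.
- **Statistical Analysis, quality of life:** 18-month scores "will be compared with ANCOVA for adjustment of effect from baseline QoL scores".

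Sample size estimation states: "Assuming an alpha value of 0.025 and a statistical power of 0.95, 49 subjects are required for each group". The analysis section states: "A p value of < 0.05 is considered statistically significant". Because these two significance levels differ, both are carried through below.

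**The concern.** A baseline variable that predicts IBC accounts for part of its variance. An unadjusted test leaves that part in the error term, so the confidence interval is wider than it need be. If the predictor is also a stratification factor, randomisation has already balanced it. The t-test's standard error then allows for a between-group imbalance that cannot arise, and the test rejects less often than its nominal level.

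The regression sentence looks like a remedy but is not one. It chooses covariates by observed imbalance, whereas the precision gain depends on how well a covariate predicts IBC. It does not define what counts as unbalanced. It also includes brace compliance, which arises after randomisation and may be affected by the assigned protocol.

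At stake is the precision of the primary estimate. This matters little at the planned effect and more if the true effect is smaller. The planned 0.8 is a discount from a pilot of 8 subjects against 8 historical controls, whose limitations the protocol acknowledges.

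**Working it through.** **Inputs from the protocol.** Effect size d = 0.8; 49 completers per group; power 0.95; alpha 0.025 (sample size) or 0.05 (analysis); pilot SDs 22.0 and 14.9. **Assumptions.** Correlation r of a baseline covariate with IBC from 0 to 0.5; a smaller true effect of d = 0.5.

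**1. Reproducing the plan's figures.** Pilot pooled SD = sqrt((22.0² + 14.9²)/2) = 18.79, and 20.0/18.79 = 1.064 (stated 1.065). Exact noncentral-t power with d = 0.8, two-sided alpha 0.025 and 49 per group is 95.2%, so the stated 49 reproduces. Design and test agree.

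**2. Adjusted power.** The unadjusted noncentrality is d × sqrt(49/2) = 0.8 × 4.950 = 3.960, with 96 degrees of freedom. With k covariate terms, divide this by sqrt((1 − r²) × (1 + k/(98 − k − 3))) and use 96 − k degrees of freedom. For k = 1 and r = 0.3: 3.960/sqrt(0.91 × 1.0106) = 4.129.

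| Alpha | d | Unadjusted | r = 0 | r = 0.2 | r = 0.3 | r = 0.5 |
|---|---|---|---|---|---|---|
| 0.05 | 0.8 | 97.5% | 97.4% | 97.8% | 98.3% | 99.5% |
| 0.05 | 0.5 | 68.8% | 68.3% | 70.1% | 72.4% | 80.3% |
| 0.025 | 0.8 | 95.2% | 95.0% | 95.8% | 96.7% | 98.8% |
| 0.025 | 0.5 | 58.0% | 57.5% | 59.4% | 62.0% | 71.4% |

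**3. Cost if the covariates predict nothing**, in power points:

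| Terms | d = 0.8, alpha 0.05 | d = 0.8, alpha 0.025 | d = 0.5, alpha 0.05 | d = 0.5, alpha 0.025 |
|---|---|---|---|---|
| 1 | 0.1 | 0.2 | 0.5 | 0.5 |
| 2 | 0.3 | 0.4 | 0.9 | 1.0 |
| 4 | 0.5 | 0.9 | 1.9 | 2.1 |
| 12 | 2.0 | 3.2 | 6.0 | 6.5 |

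Twelve terms represent one indicator per block of 10 (120/10 = 12 blocks, so 11 indicators) plus Cobb. The break-even correlation (multiple R for several terms) is about 0.10, 0.15 and 0.21 for 1, 2 and 4 terms.

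**4. Confidence interval.** The unadjusted 95% half-width is 1.985 × 18.79 × sqrt(2/49) = 7.5 IBC percentage points. With one covariate it is 7.6, 7.4, 7.2 and 6.6 at r = 0, 0.2, 0.3 and 0.5.

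**5. Size of the t-test when the predictor is stratified on.** Under perfect balance the true size at nominal 5% is P(|Z| > 1.96/sqrt(1 − r²)). This gives 4.0% at r = 0.3 and 2.4% at r = 0.5. Simulation used stratified permuted blocks of 10, two or four strata and 20,000 runs. It gave about 4% at r = 0.3. At r = 0.5 it gave 2.6% with 120 subjects and 2.8–2.9% with 98 random completers. The strata-adjusted model stayed at 4.7–5.4%. For a predictor that is not stratified on, the t-test kept its size (5.0–5.1%), so only precision is lost.

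**6. Does imbalance-selected adjustment recover the gain?** Simulated power with 98 subjects, d = 0.5, alpha 0.05, a covariate not stratified on, and 100,000 runs:

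| r | Unadjusted | Prespecified | Only if imbalance p < 0.05 | Only if imbalance p < 0.20 |
|---|---|---|---|---|
| 0.3 | 0.688 | 0.724 | 0.691 | 0.697 |
| 0.5 | 0.686 | 0.803 | 0.695 | 0.717 |

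Selection at p < 0.05 recovers about 7–8% of the gain, for example (0.691 − 0.688)/(0.724 − 0.688). Selection at p < 0.20 recovers 25–27%.

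**The case against.** The strongest reply is that nothing here is broken: the test is valid, it matches its sample size, and covariate lists usually belong in the SAP. At the planned effect and alpha 0.05, r = 0.3 moves power only from 97.5% to 98.3%. It moves the half-width from 7.5 to 7.2 points, against a design difference of about 15 (0.8 × 18.79). Larger gains need r = 0.5 or d = 0.5, and the protocol supports neither figure. Cobb is restricted to 20–40°, which may weaken any correlation. All of this stands and limits the weight of the point. It does not remove it, because the protocol makes an explicit choice of primary test, and an SAP that named a different one would contradict it.

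The quality-of-life precedent is also imperfect. There the adjustment is for the baseline of the same score, and IBC has no baseline value. That is fair: the precedent shows that ANCOVA is already in the plan, not that the plan is inconsistent.

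The protocol also does not say whether the pre-brace Cobb in the IBC formula is the baseline film or the same-visit out-of-brace film. That should be clarified, and the likely correlation depends on it. Adjusting for the baseline film is valid under randomisation on either reading.

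Finally, the planned linear regression might be meant to cover IBC. Even so, it selects on imbalance and includes compliance, so it is not the adjustment needed.

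**Conclusion.** The point holds as an inexpensive improvement. The unadjusted t-test is valid, and at worst conservative if a stratification factor predicts IBC. The planned 95% power at d = 0.8 is met.

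Prespecified adjustment for baseline Cobb pays once its correlation with IBC exceeds about 0.10. At r = 0.5 it adds 2.0 power points at d = 0.8 and 11.5 at d = 0.5 (alpha 0.05), or 3.6 and 13.4 (alpha 0.025). If Cobb predicts nothing, it costs 0.1–0.2 points at d = 0.8 and about 0.5 at d = 0.5. The correlations and d = 0.5 are assumptions, so the actual gain is unknown and may be nil. The conservatism result applies only if a real, prognostic stratification factor exists, and the protocol names none.

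**What to change.** - **Subject Randomization:** name the stratification factors, or state that there are none beyond the recruitment blocks.
- **Statistical Analysis, primary objective:** at each IBC time-point, use a prespecified linear model of IBC on group, the named factors (if any) and baseline out-of-brace Cobb. Include no term per recruitment block. Report the adjusted mean difference with its confidence interval, and keep the t-test as a sensitivity analysis.
- **Same section:** state that covariates in this primary model are not selected by observed imbalance and that brace compliance is not among them.

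The change is one of wording; no extra films or patients are needed. Each term uses one degree of freedom. The total cost with strata depends on their number, which the protocol does not give, so the factors should be settled before the model is fixed.

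### Naming Welch's t-test for in-brace correction would be a free safeguard: Student's pooled test keeps its level with the planned equal groups, but not if variances and evaluable numbers both differ

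*Protocol*

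**What the plan says.** The Statistical Analysis section of the protocol fixes the primary test, a two-sided Student's test for independent groups: "t-test will be used to compare between-group IBC". It mentions neither a variance assumption nor an unequal-variance form, and it names no confidence interval for IBC. The significance threshold is stated as "A p value of < 0.05 is considered statistically significant".

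The pilot table in part (C) of the background gives IBC of 42.1 ± 22.0 for 8 HyBP patients and 22.1 ± 14.9 for 8 historical controls. The Sample size estimation section builds on that pilot: "According to our pilot study, the effect size is 1.065", reduced to 0.8 for planning. It then states "Assuming an alpha value of 0.025 and a statistical power of 0.95, 49 subjects are required for each group". Enrolment is 60 per group, and dropout is taken to be the same in both arms: "Assuming a dropout rate of approximately 20% for each group".

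**The concern.** Student's test estimates one common variance. If the true variances differ and the groups also end up unequal in size, the pooled standard error is wrong. It is too small when the smaller group has the larger variance and too large in the opposite case. The error rate of the primary comparison would then depend on which arm lost more girls.

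Unequal evaluable numbers are possible here. HyBP involves a second, overcorrecting night brace. IBC also needs an x-ray in the daytime brace at 3 and 18 months, while bracing can end earlier through maturity, surgery or the patient's own decision. The protocol gives no figure for any difference between arms, so both its size and its direction are unknown.

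**Working it through.** **Inputs from the protocol.** Pilot SDs 22.0 and 14.9 with 8 per group; means 42.1 and 22.1; planning effect size 0.8; alpha 0.025; power 0.95; 49 evaluable and 60 enrolled per group.

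**Assumption not in the protocol.** Dropout differs by arm. The main case is 30% against 10%: 60 × 0.70 = 42 and 60 × 0.90 = 54 evaluable.

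**The plan's own figures.**
- Average SD: √((22.0² + 14.9²)/2) = 18.79. Effect size: (42.1 − 22.1)/18.79 = 1.064, against 1.065 stated.
- A two-sample noncentral-t calculation with effect 0.8, two-sided alpha 0.025 and power 0.95 gives 48.48, so 49 per group, as stated.

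**How firm the SD difference is.** The variance ratio is (22.0/14.9)² = 2.18 on 7 and 7 degrees of freedom, with F-test p = 0.33. The SD ratio is 1.48, with 95% CI 0.66 to 3.30.

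**Squared standard errors.** Student uses s²ₚ(1/n₁ + 1/n₂), where s²ₚ = [(n₁−1)s₁² + (n₂−1)s₂²]/(n₁+n₂−2). The correct value is s₁²/n₁ + s₂²/n₂. Numbers are HyBP/conventional.
- 48/48: both equal (484 + 222.01)/48 = 14.71, so the ratio is 1.
- 42/54: s²ₚ = (41 × 484 + 53 × 222.01)/94 = 336.3. Student: 336.3 × 0.04233 = 14.23. Correct: 484/42 + 222.01/54 = 15.64. Ratio of standard errors: √(14.23/15.64) = 0.954.
- 54/42: s²ₚ = (53 × 484 + 41 × 222.01)/94 = 369.7. Student: 15.65. Correct: 484/54 + 222.01/42 = 14.25. Ratio: 1.048.

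A normal approximation to the true level at nominal 0.05 is 2[1 − Φ(1.96 × ratio)]. It gives about 6.2% for ratio 0.954 and 4.0% for 1.048.

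**Simulation** (normal data, pilot SDs, 1,000,000 trials per setting):

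| HyBP/conventional | Student, nominal 5% | Student, nominal 2.5% | Welch, nominal 5% |
|---|---|---|---|
| 60/60, 49/49, 48/48 | 5.0% | 2.5% | 5.0% |
| 45/51 | 5.6% | 2.9% | 5.0% |
| 42/54 | 6.2% | 3.3% | 5.0% |
| 36/60 (40% v 0% dropout) | 7.4% | 4.1% | 5.0% |
| 54/42 | 4.0% | 1.9% | 5.0% |
| 60/36 | 3.2% | 1.4% | 5.0% |

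**Power** at the design effect (0.8 × 18.79 = 15.0 points), alpha 0.025:
- 49/49: Student 95.2%, Welch 95.1%.
- 42/54: Student 94.6%, Welch 93.1%. Student's advantage here comes with its inflated level.
- 54/42: Student 94.2%, Welch 95.4%.

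**The case against.** The strongest reply is that nothing goes wrong under the plan as written. Allocation is equal, dropout is taken as equal, and the level is then 5.0% whatever the SDs. This stands, and it limits the point.

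A reader might infer that the primary p-value and interval are wrong, or that HyBP will lose more girls and so bias the test towards false positives. The documents support neither. They give no dropout by arm, and retention calls cover both groups. If the conventional arm loses more, the test is conservative. The analysis section also promises no interval for IBC that could be wrong.

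Nor do the documents establish that HyBP has the larger variance. The pilot arms were not randomised and differed in age (13.0 against 11.7 years) and Risser grade (3.1 against 1.5). The HyBP mean Risser lies outside the trial's 0 to 2 criterion, so the SD gap may not carry over.

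The practical effect is also small. At 42/54 and the design effect of 15.0 points, t is 15.0/√14.23 = 3.98 with Student and 15.0/√15.64 = 3.80 with Welch, which leads to the same conclusion.

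It can also be said that the variance form belongs in a statistical analysis plan. That is only partly persuasive. The protocol already names Student's test, so an analysis plan naming Welch's would depart from it. The rule that switches summaries after a normality check ("The spread of data will be tested for normality") and the choice of standard errors in adjusted models can be left to that plan.

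**Conclusion.** The point holds as a minor improvement that costs nothing. With the planned equal numbers, Student's test is sound. It misses its level only if two things not established by the protocol occur together: unequal IBC variances and unequal evaluable numbers. With the pilot SDs and 30% against 10% dropout, the level at nominal 5% is about 6.2% or 4.0%, depending on which arm loses more. Welch's test stays at 5.0% in every setting examined. The size of the effect rests on normal data, on SDs from 8 patients per group and on the assumed dropout split.

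**What to change.** In the Statistical Analysis section, name Welch's unequal-variance t-test for the IBC comparison in place of Student's, and add that the mean difference between groups will be reported with its Welch confidence interval.

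This is one sentence of text. The sample size stays at 60 per group, power at 49 evaluable per group is essentially unchanged, and standard software gives the unequal-variance result beside the pooled one. Naming the form in advance also removes any choice between the two once the data are seen.
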